3.1 Study design

This is a randomized, double-blind, placebo-controlled, multicenter, parallel-group trial in approximately 180 patients with active pSS. The study is divided into 4 study periods:

Period 1: A screening period of 4 weeks to assess patient eligibility. Patients can be re-screened only once and no study-related re-screening procedure should be performed prior to written re-consent by the patient.

Period 2: At baseline, eligible patients will be randomized to one of three VAY736 dose arms (VAY736 5 mg, 50 mg or 300 mg s.c.) or a placebo arm. Blinded study drug will be administered every four weeks for a 24-week period. Approximately 45 patients will be randomized per treatment group. [REDACTED], randomization will be stratified by:

- baseline ESSDAI score (<10 or ≥ 10 based on weighted scores)

[REDACTED]

The primary endpoint will be assessed at the end of period 2 (week 24).

[figure not shown]
Treatment assignment in period 2 will remain double blinded until the end of period 3.

Period 3: After week 24 assessments, patients in the VAY736 300 mg arm will be re-randomized in a 1:1 ratio to either continue VAY736 300 mg s.c. every four weeks or switch to [REDACTED] placebo up to week 52. Patients who received placebo during period 2 will be switched to VAY736 150 mg s.c every four weeks up to week 52. Patients who received 5 mg and 50 mg s.c. in period 2 will proceed directly to period 4. Treatment assignment in period 3 will remain double blinded until the end of the study period.

Period 4: The safety follow-up period lasts for a minimum of 20 weeks from last dose administration of VAY736, or longer (with reduced visit frequency) [REDACTED]

[REDACTED] Patients who will be treated with another immunmodulatory or immunsuppressive treatment (e.g. azathioprine, cyclophosphamide, high dose glucocorticosteroids) after completion of the minimum 20 week safety follow-up period are excluded from further safety follow-up.

The primary efficacy analysis will be performed when all patients have completed the week 24 study visit. An interim analysis will occur when approximately 100 patients have completed their Week 24 visit.

Figure 3-1 Study design

*Only patients in the period 2 VAY736 300 mg arm will be eligible for period 3 re-randomization.

[figure not shown]

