- 50 mg dose arm (period 2): The unblinded pharmacist will make the necessary dilution of the solution for s.c. injection as detailed in the pharmacist's manual. The patient will receive one injection of the diluted solution for s.c. injection and one injection of generic placebo.
- 150 mg dose arm (period 3): No dilutions are necessary for this dose level. The patient will receive 1 mL of solution for injection (as after reconstitution) and another injection of generic placebo.
- 300 mg dose arm (period 2 and period 3): IRT will dispense two vials of VAY736 powder for solution. The powder will be reconstituted and the patient will receive two injections of 1 mL each, 150 mg/mL VAY736 solution for s.c. injection.

Generic placebo:

Liquid placebo [REDACTED], for s.c. injections.

Please refer to the pharmacist's manual for further instructions on reconstitution and dilution of VAY736.

Please see [Table 6-1](#) and [6-2](#) for scheduling of IRT contact and administration of study medication and pre-medication. Doses will be administered once every four weeks for 24 weeks in period 2 and once every four weeks for 28 weeks in period 3. The last doses administered in period 2 and 3 will occur on study scheduled visit 106 and 207, respectively.

For the first administration for all patients in period 2 and 3, the patient must remain at the study center for observation for at least 6 hours or longer as per local requirements.

[REDACTED]

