5.6.5 Early study termination by the sponsor

[figure not shown]
The study can be terminated by Novartis at any time for any reason. This may include reasons related to the benefit risk assessment of participating in the study, practical reasons, or for regulatory or medical reasons (including slow enrollment). Should this be necessary, the patient must be seen as soon as possible and treated as a prematurely withdrawn patient. The investigator may be informed of additional procedures to be followed in order to ensure that adequate consideration is given to the protection of the patient's interests. The investigator will be responsible for informing the Institutional Review Board/Independent Ethics Committee (IRBs/IECs) of the early termination of the trial.

6 Visit schedule and assessments

Table 6-1 lists all of the assessments and indicates with an "x" when the assessments are performed and should be documented in the eCRF. Assessments indicated with an "S" will only be documented at source.

Patients must be seen for all visits on the designated day, or as close to it as possible. Missed or rescheduled visits should not lead to automatic discontinuation. Patients who prematurely discontinue the study for any reason should be scheduled for a visit as soon as possible, at which time all of the assessments listed for the final visit will be performed. At this final visit, all dispensed investigational product should be reconciled and the adverse event and concomitant medications reconciled on the CRF.

In period 4, patients will have visits every four weeks for the mandatory 20-week safety follow-up period.

Patients who are not willing to return to the site for follow up visits in period 4, will be contacted for safety evaluations during the 30 days following the last administration of study treatment.

Table 6-1 Assessment schedule for period 1 (Screening) and period 2 (Randomized treatment period)

Period	Period 1: Screen	Period 2: Treatment					Notes
Visit	1 101 (BL)	102	103	104	105	106	199 / TD ⁷
Day	-28 1	28	56	84	112	140	168
Week	-4 0	4	8	12	16	20	24
Obtain informed consent (IC)	x						IC obtained prior to all study specific screening procedures
Demography	x						
Inclusion/exclusion	x	x					
Medical history	x						
Physical exam	S	S	S	S	S	S	
Height ¹ , weight, vital signs	x	x	x	x	x	x	1Height only collected at Screening
PhGA of overall disease activity	x	x	x	x	x	x	
ESSDAI	x	x	x	x	x	x	
Salivary flow, stimulated	x	x		x		x	

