Salivary flow, [REDACTED]	x		x		x	x	
ECG	x	x				x	
Biopsy	X ²					X ^{2, 2A}	2Performing a biopsy for the substudy is optional at both screening and end of treatment ^{2A} Optional collection of archival tissue slides at end of treatment.
Randomization	S						
Pre-medication	x						
Dosage administration record	X ³	x	x	x	x		3First dose of study medication can be administered 1 calendar day after randomization
Contact IRT	S	S	S	S	S	S	4IRT will confirm if patient will be treated in period 3 but not notify whether patient was re-randomized

Period	Period 1: Screen	Period 2: Treatment						Notes
Visit	1 101 (BL)	102	103	104	105	106	199 / TD ⁷	7If patient discontinues treatment early, safety follow up period 4 will be entered after completion of this visit
Day	-28 -1	28	56	84	112	140	168	
Week	-4 0	4	8	12	16	20	24	
Adverse Events	x	x	x	x	x	x	x	AEs include both serious and non-serious events
Renal/liver event monitoring	x	x	x	x	x	x	x	
Prior concomitant medications/procedures	x	x						
Concomitant medications/procedures	x	x	x	x	x	x	x	
Period completion/disposition form	x						x	
ESSPRI	x	x	x	x	x	x	x	
FACIT-F, SF-36 PaGA of overall disease activity and patient diary ⁵		x	x	x	x	x	x	5Diary is to be completed weekly by patient
HIV, Hep B (HBsAg, anti-HBs, anti-HBc), Hep C	x							
TB (Quantiferon/PPD)	x							
Hematology and biochemistry	x	x	x	x	x	x	x	
Serum pregnancy	x	x	x	x	x	x	x	
Urinalysis	x	x	x	x	x	x	x	
IgG, IgM	x	x	x	x	x	x	x	
Pre-dose PK sample		x	x	x	x	x	x	
Immunogenicity		x			x		x	

Period	Period 1: Screen						Period 2: Treatment						Notes
	1	101 (BL)	102	103	104	105	106	199 / TD ⁷	7If patient discontinues treatment early, safety follow up period 4 will be entered after completion of this visit				
Visit	-28	1	28	56	84	112	140	168					
Day	-4	0	4	8	12	16	20	24					
Week													

TD = Study treatment discontinuation; If patient withdraws consent (as per definition) and will not enter period 4, assessments from Table 6-3 PSD must be performed as well

X = assessment to be recorded on clinical data base

S = assessment to be recorded on source documentation only

Table 6-2 Assessment schedule for study period 3 (Extended treatment period) only for patients who continue treatment

Period	Visit	Period 3: Extended Treatment								Notes
		201	202	203	204	205	206	207	208	
Day	168	196	224	252	280	308	336	339	364	
Week	24	28	32	36	40	44	48		52	
Physical exam		S	S	S	S	S	S		S	
Weight, vital signs		x	x	x	x	x	x		x	
PhGA of overall disease activity		x	x	x	x	x	x		x	

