7.2.2 SAE reporting

To ensure patient safety, every SAE, regardless of causality, occurring after the patient has provided informed consent and until 30 days after the last study visit must be reported to Novartis within 24 hours of learning of its occurrence. Any SAEs experienced after the 30 day

period after the last study visit should only be reported to Novartis if the investigator suspects a causal relationship to study treatment.

All follow-up information for the SAE including information on complications, progression of the initial SAE and recurrent episodes must be reported as follow-up to the original episode within 24 hours of the investigator receiving the follow-up information. An SAE occurring at a different time interval or otherwise considered completely unrelated to a previously reported one must be reported separately as a new event.

Information about all SAEs is collected and recorded on the Serious Adverse Event Report Form; all applicable sections of the form must be completed in order to provide a clinically thorough report. The investigator must assess the relationship of each SAE to each component of study treatment (VAY736/placebo or methylprednisolone premedication) complete the SAE Report Form in English, and submit the completed form within 24 hours to Novartis. Detailed instructions regarding the submission process and requirements for signature are to be found in the investigator folder provided to each site.

Follow-up information is submitted as instructed in the investigator folder. Each re-occurrence, complication, or progression of the original event must be reported as a follow-up to that event regardless of when it occurs. The follow-up information should describe whether the event has resolved or continues, if and how it was treated, whether the blind was broken or not, and whether the patient continued or withdrew from study participation.

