### **Period**

The period 2 starts from the first dose on Day 1 visit; the period 2 end date is the end of treatment date in period 2. The period 3 starts from first dose in period 3; the period 3 end date is defined as the end of treatment date in period 3. The period 4 starts on the day after the end of treatment in period 2/3. Assignment of events to each period will be based on date and time. When time is missing or not reported, the assignment will be based on date only; in that case, events starting on the date of first dose in period 3 will be assigned to the period 3 for those who are entering period 3, or to the safety follow-up period.

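### Patients who decline period 4 visits have planned safety contact only to 30 days after last dose, leaving a nominal completer about 110 of the 140 minimum follow-up days without planned enquiry

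*Protocol*

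**What the plan says.** Protocol Section 6 (Visit schedule and assessments) sets the rule: "In period 4, patients will have visits every four weeks for the mandatory 20-week safety follow-up period". It then gives a fallback: patients not willing to return to the site in period 4 "will be contacted for safety evaluations during the 30 days following the last administration of study treatment".

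Three different anchors are in use:

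- **Last VAY736 dose.** Section 3.1: "The safety follow-up period lasts for a minimum of 20 weeks from last dose administration of VAY736".
- **Last study treatment.** The Section 6 fallback. By the glossary, study treatment includes placebo.
- **Last study visit.** Section 7.2.2 requires every SAE, whatever its cause, occurring from consent "until 30 days after the last study visit must be reported to Novartis within 24 hours".

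Section 5.5.4 fixes the last doses: "The last doses administered in period 2 and 3 will occur on study scheduled visit 106 and 207, respectively". In the SAP (Section 2.1.1, Period), "The period 4 starts on the day after the end of treatment in period 2/3".

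**The concern.** The fallback is written for period 4, yet its clock starts about four weeks before a completer gets there. It has almost run out when period 4 opens.

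The patients concerned can still be reached. Under Section 5.6.3, withdrawal of consent requires both an unwillingness to take part and a refusal of further data collection; declining site visits is not enough. Section 5.6.4 does not allow a patient to be called lost to follow-up until the scheduled end-of-study visit has passed. Section 5.5.6 wants patients who are off drug encouraged to stay in period 4. A 30-day limit on planned contact fits none of these well.

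The protocol itself expects effects to matter for longer: contraception for 4 months after stopping (exclusion criterion 19), pregnancy testing up to 1 year after last dose (Section 6.5.6), and discharge only at two years for patients whose B cells have not recovered (SAP Section 1.1). Infection and late-onset neutropenia are named topics in Section 3.6. At stake is how completely adverse events after treatment are captured, and whether the patients missed differ from those who keep attending. The gap would show in the SAP's long-term safety summary (grouping scheme 2), which spans all periods.

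**Working it through.** **Inputs**

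- Table 6-1, day row: "Day -28 1 28 56 84 112 140 168". Visit 106 is day 140; visit 199 (week 24) is day 168.
- Table 6-2, day row: "Day 168 196 224 252 280 308 336 339 364". Visit 207 is day 336; week 52 is day 364.
- Table 6-3: visits 301 to 304 fall at weeks 28, 32, 36, 40 after period 2 and weeks 56, 60, 64, 68 after period 3.
- Section 5.5.5: a dose may move by up to 1 week for administrative reasons, and one dose may be missed in each treatment period.

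**Step 1. Reproduce the plan's 20 weeks (last dose + 140 days)**

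- Period 2: 140 + 140 = day 280 = week 40.
- Period 3: 336 + 140 = day 476 = week 68.

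Both equal visit 304, so the schedule agrees with 20 weeks counted from last dose.

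**Step 2. Where the fallback ends (last dose + 30 days)**

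| | Period 2 completer | Period 3 completer |
|---|---|---|
| Contact ends | 140 + 30 = day 170 | 336 + 30 = day 366 |
| End-of-period visit | day 168 | day 364 |
| Difference | 2 days | 2 days |
| Period 4 starts (SAP) | day 169 | day 365 |
| Visit 301 | 28 × 7 = day 196 | 56 × 7 = day 392 |

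None of visits 301 to 304 falls inside the window.

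**Step 3. Share of the minimum covered, counted from last dose**

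30 / 140 = 21% covered; 140 − 30 = 110 days (15.7 weeks, 79%) with no planned contact.

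**Step 4. How far this depends on dose dates (period 2; period 3 gives the same differences)**

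- Last dose 7 days early: 133 + 30 − 168 = −5 days.
- Last dose 7 days late: 147 + 30 − 168 = +9 days.
- Last scheduled dose is the permitted missed one: 112 + 30 − 168 = −26 days. The minimum then ends at 112 + 140 = day 252, so 252 − 168 = 84 days follow the week 24 visit without planned contact.

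**Step 5. Groups to which the 110 days do not apply**

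- *Early discontinuers.* Table 6-1, note 7, takes them into period 4 after the treatment discontinuation visit. If that visit is d days after last dose, 30 − d days of contact fall inside period 4. As an illustration, d = 7 gives 23 days.
- *300 mg re-randomized to placebo.* Their last VAY736 dose is nominally day 140, so the Section 3.1 minimum ends on day 280 (week 40), inside period 3. For them it is met before period 4.

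**Step 6. Compare with the SAE window**

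If the end-of-period visit is the last one attended, Section 7.2.2 runs to 168 + 30 = day 198 or 364 + 30 = day 394. That is 28 days beyond planned contact.

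**The case against.** The best defence is that the sentence adds contact for people who cannot be made to attend and does not end any other duty. Patients who stop during follow-up are asked for an end-of-study visit (Section 5.6.2), and Section 6 asks for a final visit with adverse events reconciled. Patients are told to report later events they think are related, and detected events are followed up (Section 7.1). SAEs suspected to be related are reportable without a time limit (Section 7.2.2), and every pregnancy after consent is reportable (Section 7.6). All this stands. But each provision depends either on someone volunteering information or on a site visit the patient may decline. None is planned enquiry, so the gap stays open.

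Several stronger readings are tempting, and the documents do not support them:

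- *That follow-up is lost, or that nobody asks these patients anything.* The text sets no end to other data collection, and 30 of the 140 days are covered.
- *That the fallback is empty.* Early discontinuers who move to period 4 soon after last dose have much of the window inside it.
- *That only 2 of 112 days (1.8%) are covered.* This counts from the end-of-period visit, whereas Section 3.1 counts from last dose.
- *That day 476 applies to everyone in period 3.* It does not apply to those switched from 300 mg to placebo.
- *That Section 6 contradicts Section 7.2.2.* One governs planned contact, the other what a site reports once it knows of an event. Both can be followed; their anchors simply differ.
- *That a given number of patient-years disappears.* The documents give no refusal rate, so any such total is an assumption.
- *That phase 3 dose choice is compromised.* Sections 3.5 and 9.7 tie that planning to the interim and week 24 analyses.

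Section 3.6 reports no late-onset neutropenia and no infection-related SAEs with VAY736 at the time of writing, though parts of that text are redacted.

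**Conclusion.** The point holds as a gap in planned safety enquiry. A nominal completer whose last dose was VAY736 and who declines period 4 visits has no planned contact for about 110 of the 140 minimum days and for all of visits 301 to 304. The 2-day overlap with period 4 is nominal and ranges from −5 to +9 days with the permitted dose shift.

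This rests on two assumptions: that the fallback is the only planned contact for these patients, since no other is described, and that visits and doses fall on their scheduled days. How many patients would be affected, and whether they would be sicker than the rest, cannot be determined from the documents.

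The consequence is incomplete, possibly selective, post-treatment safety data. The primary endpoint and the 24-week safety comparison (SAP grouping scheme 1, which stops at the end of period 2 treatment) are untouched. A reader might infer that this must be fixed before the trial can be relied on; it does not reach that level. Severity is minor to moderate.

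**What to change.** Reconcile Sections 3.1, 6 and 7.2.2, stating how the three anchors (last VAY736 dose, last study treatment, last study visit) relate for each group, including patients switched from 300 mg to placebo. In Section 6, state that patients who decline site visits but have not withdrawn consent have remote enquiry for AEs, SAEs, pregnancy and concomitant medication through the 20-week minimum that the protocol already sets.

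The cost is protocol wording and a few telephone calls per such patient, with no added visits or samples. The limit should be stated too: calls cannot replace laboratory monitoring, so a fall in neutrophils without symptoms would still be missed in these patients.

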6.1 Information to be collected for screen-failed patients

All patients who have signed informed consent but not entered into the next period will have the study completion page for the screening period, demographics, inclusion/exclusion, and serious adverse event (SAE) data collected. Adverse events that are not SAEs will be followed by the investigator and collected only in the source data.

6.2 Patient demographics/other baseline

Patient demographic and baseline characteristic data to be collected on all patients include: date of birth, age, sex, race, ethnicity, source of patient referral, relevant medical history/current medical condition present before signing informed consent where possible, diagnoses and not symptoms will be recorded.

Investigators will have the discretion to record abnormal test findings on the medical history CRF whenever in their judgment, the test abnormality occurred prior to the informed consent signature.

The following assessments are to be done at screening only and will not be repeated after the patient starts with study treatment.

6.2.1 Screening for Hep B, Hep C and HIV

- All patients will be screened for hepatitis B surface antigen (HBsAg), anti-HBs, and anti-HBc. Patients testing positive for any of the serologic markers will not be eligible for randomization, with the exception of anti-HBs due to previous vaccination against Hep B. [Table 19-1](#) in Appendix 7 provides detailed Hep B serology result interpretations.
- Screening for hepatitis C will be based on HCV antibodies.
- Evaluation for HIV seropositivity will be performed, and, if positive, confirmation by a second technique available at the laboratory site, e.g., Western blot.

Appropriate counseling will be made available by the Investigator in the event of a positive finding. Results will be available as source data and will not be recorded within the CRF.

All samples will be shipped to the central laboratory.

6.2.2 Screening for Tuberculosis

Determination of the tuberculosis (TB) status will be required before administration of study treatment and should be performed as defined by local guidelines. The TB status must be determined by medical history, signs, symptoms, TB testing (QuantiFERON-TB Gold assay or, if per local requirement only, a purified protein derivative [PPD] test may be performed instead of Quantiferon).

Quantiferon

If the test result is negative, the patient may be randomized.

If the test result is positive, the investigator should perform workup for the test result as per local procedures. If a TB workup was conducted prior to screening the patient, results of the

workup can be used to assess eligibility if the workup was conducted within 12 weeks prior to randomization.

If the test result is indeterminate, the investigator may repeat the test once or may proceed directly to perform workup for the test result as per local procedures. This action is at the discretion of the investigator. If the second test is negative, the patient may be randomized.

If the second test is positive or indeterminate, the investigator should perform workup as per local guidelines.

PPD skin test

PPD skin test will be performed as an alternative to Quantiferon in accordance with local guidelines and read at screening or within 6 months prior to randomization in order to evaluate an eventual infection with tuberculosis. The test dose is bioequivalent to 5 tuberculin units (or as according to local standard practice) of standard PPD injected intradermally into usually the volar surface of the forearm. The site is cleansed and the PPD extract is then injected into the most superficial dermal layer of the skin. If given correctly, the injection should raise a small wheal of about 5 mm, which resolves within 10-15 minutes.

Because the reaction (induration) will take 48-72 hours to develop, the patient must return to the investigators' site within that time for a proper evaluation of the test site. This will determine whether the patient have had a significant reaction to the PPD test. A reaction is measured in millimeters of induration (hard swelling) at the site. A PPD skin induration ≥ 5 mm is interpreted as positive result.

Precautions against tuberculosis should be handled according to the best medical practice consistent to the local standards in each country with prior consultation with Novartis.

Patients requiring administration of antibiotics against latent tuberculosis should complete their treatment and should be considered cured prior to being re-considered for entry into this study (consultation with Novartis must occur before allowing the patient to enter the study).

Patients testing positive for latent TB per workup may be randomized to the trial if sufficient treatment has been completed according to local routine clinical practice. Patients testing positive for active TB per workup are not eligible for the study. Patients testing negative for TB (no signs of latent or active TB) per workup may be randomized to the trial.

6.2.3 pSS medical history and previous therapies

The date of first diagnosis of pSS will be collected from the patient's medical history. History of any other connective tissue disorders must be recorded on the Disease Diagnosis eCRF.

If the patient had previously received biologics for treatment of Sjögren's syndrome, the medications received must be recorded on the prior medications - pSS Specific Biologic Treatments eCRF. These may include infliximab, etanercept, rituximab, ocrelizumab, epratuzumab, belimumab, alefacept and abatacept.

If the patient was previously treated with another disease modifying or immunosuppressive therapy for Sjögren's syndrome, these must be recorded on the 'Prior Medications – pSS

specific Non-biologic Treatment' eCRF. These treatments may include: hydroxychloroquine, methotrexate, azathioprine, mycophenolate, cyclophosphamide and chlorambucil.

